Study Protocol and

Statistical Analysis Plan (SAP)

DEVELOPMENT AND PRELIMINARY TESTING OF A NON-REGULATED DIGITAL SERVICE THAT SUPPORTS COGNITIVE BEHAVIORAL THERAPY FOR DEPRESSIVE SYMPTOMS UNDER CLINICAL SUPERVISION

Principal Investigator:	[name] Chief of Psychology Massachusetts General Hospital & Harvard Medical School Boston, MA, United States of America
Ethical approval:	Mass General Brigham Institutional Review Boards (protocol # 2020P001958, approved on 04/08/2021)
ClinicalTrials.gov identifier:	NCT05386329
Funding:	This study was funded by Koa Health (formerly Telefonica Alpha). Investigators from MGH developed the Mindset app in collaboration with technologists and designers from Koa Health via a user-centered, iterative design approach. The investigators from MGH were responsible for the study design and for the execution of the study; authors from Koa Health supported the technical activities related to the development and deployment of the app, and provided funding for the project. Koa Health had no role in the recruitment of participants and had no access to data during the trial.
Document Date:	November 14, 2023 (shortened version) Last IRB-approved update: 09/19/23
Author	[name], MApStat Assistant Professor of Psychology Massachusetts General Hospital & Harvard Medical School Boston, MA, United States of America
Version	Draft 1.0

PRELIMINARY TESTING OF COMBINED DIGITAL COGNITIVE BEHAVIORAL THERAPY PLUS VIRTUAL TREATMENT FOR DEPRESSIVE SYMPTOMS

I. SPECIFIC AIMS

The overarching purpose of this project is to conduct an open trial to test the efficacy of digital CBT for when combined with virtual visits with a CBT therapist. Specifically, we seek to evaluate how digital CBT plus virtual treatment initially performs when deployed in a clinical setting to support treatment. This treatment will include the mobile CBT for depression app in combination with eight virtual visits delivered by doctoral-level psychologists or psychology interns with their master's degree over a period of 8 weeks. The therapist will be assigned once eligibility is determined and will offer 8 virtual treatment sessions in total in addition to unlimited access to the app. All virtual sessions will be no longer than 16-25 min. The combined CBT app plus virtual treatment will be tested in 28 patients.

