Hypothesis 2b: We hypothesize that participants receiving digital CBT plus virtual treatment will evidence statistically significant improvement on secondary clinical outcome measures (i.e., functional impairment (WSAS) and quality of life (Q-LES-Q)) from baseline to post-treatment (week 8).

C. Statistical methods

Primary endpoints: feasibility and acceptability of the combined digital CBT plus virtual treatment.

Analysis:

We will examine feasibility (H1a) and acceptability (H1b) by reporting:

- 1. Refusal and dropout rates and reasons
- 2. Patient satisfaction, as measured by the Client Satisfaction Questionnaire
- 3. Patient feedback, as measured by Mobile Application Rating Scale user version
- 4. Patients' credibility and expectancy ratings for the open-label treatment, as measured by the Credibility/Expectancy Questionnaire
- 5. Treatment utilization, as measured by the Treatment Utilization Questionnaire

Secondary endpoints: preliminary efficacy of digital CBT plus virtual treatment for reducing severity of depression symptoms, and improving quality of life and functional impairment

Analysis:

Intention-to-treat mixed model analyses with repeated measures (baseline, mid-treatment, post-treatment) will be used to examine differences between pre- and post-treatment depression (HAM-D scores), using a two-tailed α -level of .05. The pre- to post-treatment effect size will be calculated. Similar analyses will also be conducted for change in functional impairment (WSAS) and quality of life (Q-LES-Q) over the course of treatment. We will not adjust for multiple testing among secondary outcomes based on the recommendation of Cook and Farewell (1996), who argue that multiplicity adjustments are not necessary if separate test results are interpreted marginally and address different aspects of the patient experience and decision-making process rather than alternative assessments of efficacy.

D. Power analysis

With n=28, we will have > 80% power to detect pre- to post-treatment effect sizes of d \ge 1.37 (very large effect sizes). The estimate of the detectable effect size is based on a single degree of freedom contrast in a paired means test, implemented in SAS for Windows version 9.4. The

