power model used a two-sided alpha=0.05, a power of 0.80, assumed a pre- to-post-treatment correlation of 0.18, and a doubling of the standard deviation from pre- to post-treatment. The pre- to post-treatment correlation estimate was based on the mean pooled correlation between pre-test and post-test HAM-D scores in 14 CBT trials for adult depression (Cuijpers et al., 2016); with higher pre-post correlations, smaller effect sizes would be detectable in other secondary outcomes. The anticipated increase in outcome standard deviation was based on observations reported in treatment studies with participants with MDD, which reported pre- to post-treatment standard deviation increases in observed HAM-D scores in the range of 161-191% (Jarrett et al., 1999; Elkin et al., 1989; Goldberger et al., 2011). We further assumed no drop-out by the end of treatment, similar to what we observed in pilot studies for similar app-treatment for body dysmorphic disorder ([name] et al., 2020); if drop-out was 20%, we would only be able to detect effect sizes of $d \ge 1.55$. For comparison, in a meta-analysis of randomized controlled treatment trials that included internet CBT (iCBT) for persons with MDD (Andrews et al., 2018), the observed median percentage of participants randomized who finished the treatment course was 66% (50/64 trials) and the interquartile range was 29% (Q1 52%, Q3 80%). Large pre-to post-treatment effect sizes for CBT treatments among patients with MDD are to be expected, based on a meta-analysis by Cuijpers and colleagues (2016), which found that the mean pre-post standardized mean difference (i.e., effect size) in 14 CBT trials was 1.79, 95% CI: [1.37, 2.21].

VII. RISKS AND DISCOMFORTS

A. Complications of surgical and non-surgical procedures

Not applicable

B. Drug side effects and toxicities

Not applicable

C. Device complications/malfunctions

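### The power inputs in VI.D give a detectable d of about 1.14 at n=28 and 1.30 after 20% drop-out (baseline-SD units), not the stated 1.37 and 1.55; the error is conservative

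*Combined protocol and SAP*

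**What the plan says.** The enrolment target is 28 throughout; Section I (Specific Aims) says "The combined CBT app plus virtual treatment will be tested in 28 patients". Section VI.D (Power analysis) then states "With n=28, we will have > 80% power to detect pre- to post-treatment effect sizes of d" ≥ 1.37. It describes this as an estimate of the detectable effect size, "based on a single degree of freedom contrast in a paired means test".

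The inputs follow: "power model used a two-sided alpha=0.05, a power of 0.80", and then, in full, "a power of 0.80, assumed a pre- to-post-treatment correlation of 0.18, and a doubling of the standard deviation from pre- to post-treatment". The SD assumption is supported by cited studies reporting "standard deviation increases in observed HAM-D scores in the range of 161-191" percent.

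The base case assumes that nobody drops out. The sensitivity case reads "if drop-out was 20%, we would only be able to detect effect sizes of" d ≥ 1.55. The paragraph closes with a benchmark: the mean pre-post effect "in 14 CBT trials was 1.79, 95% CI: [1.37, 2.21"].

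The plan does not say which SD is used to standardise d.

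**The concern.** A detectable effect follows by arithmetic from the sample size, alpha, power, correlation and SD ratio. All five are stated, so both figures should be reproducible. Neither is.

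The drop-out message is the part with practical content. As written, losing 20% of patients moves the threshold to 1.55, above the lower confidence limit of 1.37 in the plan's own benchmark. A reader would conclude that the trial becomes underpowered at the low end of the expected range. The zero-drop-out base case is also the less plausible one: the plan says elsewhere that it expects drop-outs, and VI.D cites a median completion of 66% in internet-CBT trials.

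The unnamed standardiser adds to the problem. If the SD is assumed to double, a d in baseline SDs is twice the same change expressed in post-treatment SDs. The figures then cannot be compared with 1.79 unless the unit is known.

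**Working it through.** **Inputs (all from VI.D).** n = 28; paired test; two-sided alpha 0.05; power 0.80; r = 0.18; SD post/pre = 2. Drop-out of 20% leaves 28 × 0.8 = 22.4, taken as 22 (23 also shown). Assumption: d is in baseline-SD units.

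**Step 1. SD of the change, with baseline SD = 1.**

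SD_diff = √(1² + 2² − 2 × 0.18 × 1 × 2) = √4.28 = 2.069.

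**Step 2. Standardised change d_z needed for 80% power.** Exact noncentral t, df = n − 1, noncentrality d_z√n.

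**Step 3. Convert to baseline SDs: d = d_z × 2.069.**

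| n | d_z | d | Plan states |
|---|---|---|---|
| 28 | 0.5492 | 1.136 | 1.37 |
| 23 | 0.6113 | 1.265 | 1.55 |
| 22 | 0.6264 | 1.296 | 1.55 |

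The plan's figures are not reproduced.

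**Step 4. Power at the plan's own figures.**

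- d = 1.37, n = 28: d_z = 1.37/2.069 = 0.662; noncentrality 0.662 × √28 = 3.50; power 92.2%.
- d = 1.55, n = 22: d_z = 1.55/2.069 = 0.749; noncentrality 0.749 × √22 = 3.51; power 91.8% (93.0% at n = 23).
- d = 1.37, n = 22: noncentrality 0.662 × √22 = 3.11; power 84.2% (85.9% at n = 23).
- d = 1.79: power 99.3% at n = 28 and 97.2% at n = 22.

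**Step 5. Does another reading give 1.37 and 1.55?**

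| Variant | n=28 | n=22 |
|---|---|---|
| Normal approximation | 1.095 | 1.236 |
| Average-SD units (divide by 1.5) | 0.76 | 0.86 |
| Root-mean-square SD units (divide by √2.5) | 0.72 | 0.82 |
| Post-treatment-SD units (divide by 2) | 0.57 | 0.65 |
| Cited range as post/pre ratio, 1.61 to 1.91 | 0.95–1.09 | 1.09–1.25 |
| Cited range as an added increase, ratio 2.61 to 2.91 | 1.44–1.59 | 1.64–1.82 |
| Power 0.90 | 1.315 | 1.500 |
| Correlation −0.18 | 1.314 | 1.498 |

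None does. Two departures from the stated inputs come close:

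- An SD ratio of 2.47 gives 1.37 at n = 28 and 1.56 at n = 22; a ratio of 2.45 gives 1.55 at n = 22. Both contradict the stated doubling.
- The stated inputs with other sample sizes: n = 20 gives 0.6604 × 2.069 = 1.366, and n = 16 (20 less 20%) gives 0.7495 × 2.069 = 1.551. Neither sample size appears in the documents.

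**The case against.** The case for leaving the paragraph alone has several parts.

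- **The main sentence is true.** It claims more than 80% power at d ≥ 1.37, and power there is 92%. This stands for that sentence. It does not cover the text that gives 1.37 as the detectable effect at a power of 0.80, nor the claim that *only* d ≥ 1.55 would be detectable after drop-out.
- **Nothing depends on the figures.** The primary endpoints are feasibility and acceptability, reported descriptively. VI.D describes what 28 patients can detect and does not derive the 28. The error is on the safe side. All of this stands, and it limits the importance of the point.
- **The plan itself never compares 1.55 with the lower limit of 1.37.** It relies on the mean of 1.79, which exceeds both the stated and the recomputed threshold. This also stands. The comparison is one a reader would naturally make from the adjacent numbers, and it is valid only if both d values use the same standardiser, which the documents do not say.
- **Baseline SD is an assumption.** True, so 1.14 and 1.30 depend on it. The failure to reproduce 1.37 does not, because the other three standardisers move further away.
- **The planned analysis is a mixed model with a week-4 measurement, and patients who drop out are still asked to attend assessments.** The paired-test powers are therefore not the power of that analysis. The plan made the same simplification, so comparing like with like is fair.

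**Conclusion.** The point holds. On the stated inputs and in baseline-SD units, the 80%-power threshold is 1.14 rather than 1.37 with 28 patients, and 1.30 (1.26 if 23 remain) rather than 1.55 after 20% drop-out. The stated thresholds are about 20% too high (1.37/1.136 = 1.21; 1.55/1.296 = 1.20), and true power at them is about 92%.

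The error is conservative: the trial can detect smaller effects than it claims. Its one misleading consequence is the drop-out sentence. If the benchmark d is in the same units, 22 patients still give 84% power at its lower limit of 1.37. Even 66% completion (28 × 0.66 = 18.5, so 18 patients) puts the threshold at 0.7007 × 2.069 = 1.45, below the 1.55 that the plan attaches to 20% loss.

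The match at n = 20 and n = 16 suggests figures carried over from a smaller sample. That is an inference, and the documents do not confirm it.

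**What to change.** Confirm the inputs and name the standardiser. If the inputs are as printed, reword VI.D along these lines: with 28 patients there is 80% power to detect a pre-post change of d ≥ 1.14 in baseline-SD units (d_z = 0.55); with 20% missing at week 8 (22 patients), d ≥ 1.30. If other inputs were used, state the SD ratio, correlation, standardiser, power and sample size so that 1.37 and 1.55 can be reproduced, and reconcile them with the stated doubling of the SD. Also say whether 161-191% is a ratio or an increase.

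The cost is one reworded paragraph. No extra patients are needed and the analysis does not change.
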